1. TITLE

Vaper to Vaper (V2V): A Multimodal Mobile Peer Driven Intervention to Support Adolescents in Quitting Vaping

2. EXTERNAL IRB REVIEW HISTORY*

None.

3. PRIOR APPROVALS:

None.

4. OBJECTIVES*

In this study, we will develop Vaper-to-Vaper (V2V), a suite of mobile peer driven tools, including peer texting and coaching, based on lessons learned in our prior tobacco intervention work. These tools will engage and help adolescents use strategies to manage cravings and successfully quit e-cigarettes. The specific aims of the V2V study are to:

Aim 1: Adapt the existing peer-driven and gamification mobile tools to develop the V2V intervention.

1A. Conduct a qualitative study to (1) explore issues unique to e-cigarette use (e.g., concerns, motivations, triggers, symptoms of nicotine dependence), and (2) understand perceived needs for cessation support (preferences for technology (e.g., texting, app-based) to inform adaptation of the toolset.

1B. Work with these users to build the V2V innovations, including peer messaging for adolescents, peer-to-peer videos, and game narratives for gamification.

1C. Refine the V2V mobile toolset with iterative usability testing (mini-pilot).

There are no hypotheses for Aim 1. Aim 1 is just to adapt the existing peer-driven and gamification mobile tools to develop the V2V intervention.

Aim 2: Evaluate the feasibility of the research protocols and the feasibility and acceptability of the V2V intervention (peer messaging, peer coaching, and gamification) compared to e-cigarette cessation written materials (control) in a pilot feasibility study.

2A. Assess the feasibility of the research protocols, including participant recruitment and retention.

***Hypothesis H1:** We will be able to recruit 80 adolescents (20/school, 40 per study condition), and $\geq 85\%$ will be retained in each study condition at 6-month follow-up.*

2B. Monitor V2V engagement (e.g., number of responses to texting quizzes, peer coaching interactions, peer videos viewed) and assess acceptability of and satisfaction with the program.

2C. Assess preliminary effect size estimates of the V2V intervention on cotinine-validated 7-day point prevalence abstinence, time to first quit attempt, and amount of use.

***Hypothesis H2:** The intervention will be associated with greater cotinine-validated 7-day point prevalence vaping abstinence rates, lower time to first quit attempt, and less amount of e-cigarette use compared to control at 6-month follow-up.*

5. BACKGROUND*

Adolescent e-cigarette use has now exceeded combustible cigarette use, leading the FDA and the U.S. Surgeon General to call the increasing use of e-cigarettes among U.S. adolescents an epidemic.¹⁻⁴ The 2018 National Youth Tobacco Survey found a 78% increase in e-cigarette use in just one year,⁵ with over 3.5 million youth currently using e-cigarettes. Alarmingly, 28% of high school e-cigarette users are vaping on 20 or more days in the past month.⁵ The high amounts of nicotine in e-cigarettes harm adolescent brain development, impacting learning,

memory, attention, mood, and impulse control.⁶ Further, adolescent e-cigarette users are at higher risk than non-users of transitioning to traditional cigarettes.^{1,2,6-10} Tobacco use continues to be the leading cause of preventable morbidity and mortality in the U.S., with nearly all tobacco use beginning during youth and young adulthood.^{11,12} Once transitioned, 80% of these adolescent smokers will continue to smoke into adulthood and, of those, one-half will die 13 years earlier than nonsmoking peers.^{13,14}

Evidence-based and accessible e-cigarette cessation interventions are critically needed to help adolescent e-cigarette users quit.^{1,2,7} To our knowledge, there are currently no evidence-based interventions to assist adolescent e-cigarette users in quitting.^{1,2,7} E-cigarette users are a complex group, including all race and ethnic groups as well as youth of higher and lower socioeconomic status (SES).¹⁵ Although recent concerns regarding vaping and proposed regulatory changes (increasing purchasing age, banning flavors) may increase adolescent interest in quitting and demand for e-cigarette cessation interventions, the perception of lower risk of e-cigarettes may lead to a lower intention to quit,^{16,17} with the majority of youth e-cigarette users believing vaping only includes flavoring and not nicotine.¹⁸ Therefore, novel approaches specifically tailored to their unique needs that can be disseminated broadly are required to engage, educate, motivate, and support adolescent e-cigarette users to successfully quit.

Although rates are higher among adolescents in higher SES groups, rates have increased among lower SES groups also. For example, in a recent national online survey of youth aged 13 to 18 between August and October 2017, weighted to be representative of the overall U.S. population, 43% of adolescents who were from lower SES groups indicated that they were current e-cigarette users.¹⁹ Lower SES groups also have lower perceived health risks of e-cigarettes.²⁰ If we do not appropriately address lower SES groups, we may end up in a similar situation to combustible cigarette use in which disparities have expanded considerably.^{20,21} To date, higher SES groups have benefited more from smoking cessation interventions and their rates are considerably low, whereas rates among lower SES groups are considerably higher. Research addressing and boosting treatment potency among health disparities populations is also of considerable interest to NIDA as stated in the PAR (PAR-19-213).²² Consequently, we decided to target lower SES groups in our study to prevent these disparities in the future.

The V2V multi-modal mobile peer driven intervention adapts our innovative, existing mobile technology into an e-cigarette cessation program for adolescents, creating a highly accessible, engaging and disseminatable treatment option. Delivery of treatment via multi-modal mobile technology may improve efficacy by providing adolescents coaching and support in considering quitting if they are not yet ready, and in quitting when ready, within their real-world contexts. The use of multi-modal mobile technology overcomes many of the challenges youth experience in accessing treatment for their nicotine dependence, potentially increasing reach and creating a highly accessible and disseminatable treatment option.

6. INCLUSION AND EXCLUSION CRITERIA*

Aim 1 Study Population (20 adolescent e-cigarette users (Peer Advisory Panel) and two key informants)

The study population will be derived from 20 adolescent e-cigarette users in one high school selected for its high rate of racial/ethnic minorities and low SES status. We will also recruit two key informants (school nurse and Vice Principal) from the same high school.

Inclusion criteria for peer advisory panel: (1) enrolled in grade 9-12 at a local high school; (2) current e-cigarette user; (3) have a smartphone; and (4) English- or Spanish-speaking. Current e-cigarette user is defined as a response greater than “0 days” to the question: “During the past 90 days, on how many days did you use e-cigarettes?” This eligibility criterion is modeled on a question in the 2018 National Youth Tobacco Survey (NYTS), a survey of U.S. middle and high school students which used a 30-day timeframe.

Exclusion criteria for peer advisory panel: (1) unable or unwilling to provide informed assent or consent (in the case of those aged 18 years or older).

Inclusion criteria for two key informants: (1) employed as a school nurse or Vice Principal at the Aim 1 high school.

Exclusion criteria for two key informants: (1) unable or unwilling to participate in the study.

Aim 2 (80 adolescent e-cigarette users and up to 12 key informants)

In Year 2 of the project, 80 adolescent e-cigarette users in 4-7 high schools selected for their high rates of racial/ethnic minorities and low SES status (20/school, 40/study condition) will be recruited and complete assessments at baseline and 6-month follow-up.

Inclusion criteria for 80 adolescent e-cigarette users: (1) enrolled in grade 9-12 at a participating high school; (2) current e-cigarette user; (3) have a smartphone; and (4) English- or Spanish-speaking. Current e-cigarette use is defined as a response greater than “0 days” to the question: “During the past 90 days, on how many days did you use e-cigarettes?” This eligibility criterion is modeled on a question in the 2018 National Youth Tobacco Survey (NYTS), a survey of U.S. middle and high school students which used a 30-day timeframe.

Exclusion criteria for 80 adolescent e-cigarette users: (1) unable or unwilling to provide informed assent or consent (in the case of those aged 18 years or older).

Inclusion criteria for key informants: (1) employed as a school nurse, Vice Principal, or other academic administrator at a participating high school.

Exclusion criteria for key informants: (1) unable or unwilling to participate in the study.

Vulnerable Populations

Pregnant Women

Pregnant women may be included in this study as an incidental population.

Adults Unable to Consent

Adults unable to consent will not be included in the study population.

Prisoners

Prisoners will not knowingly be included in the study population.

Children

We will be recruiting adolescents in grades 9 through 12, aged 13-19 years old. The rationale for targeting adolescents in this study is that the FDA and the US Surgeon General call the increasing use of e-cigarettes among U.S. adolescents an epidemic, with e-cigarette use exceeding combustible cigarette use. The high amounts of nicotine in e-cigarettes harm adolescent brain development, impacting learning, memory, and attention. Adolescent e-cigarette users also are at higher risk than non-users of transitioning to traditional cigarettes. We are therefore interested in applying lessons learned in developing interventions for adolescents and another challenging population, low motivated adult smokers. Study investigators have extensive experience with conducting research with adolescents and a reputation for designing culturally sensitive, patient-centered programs, and we are accountable to those standards. Please see Section #11, *Procedures Involved*, and Section #30, *Consent Process*, for more information.

We will include English- and Spanish-speaking individuals in this study. Should the intervention be proven efficacious, we will apply for further funding and plan to include additional non-English speaking populations in future studies.

7. STUDY-WIDE NUMBER OF SUBJECTS*

N/A; this is not a multi-site study.

8. STUDY-WIDE RECRUITMENT METHODS*

N/A; this is not a multi-site study.

9. STUDY TIMELINES*

The overall project timeline is described in the table below (Table 1):

Table 1. Project Timeline

This study is planned to take place over the course of two years. Primary analysis is expected to be complete by the end of year two.

Duration of an Individual Subject's Participation

Aim 1 adolescent participants (peer advisory panel) are expected to actively participate in the study for no more than one month. The peer advisory panel members will be invited to participate in four activities: 1) Semi-structured interview and brief survey; 2) Text message writing activity; 3) Peer video activity; and 4) Meaningful stories writing session. The semi-structured interview for adolescent participants is expected to last 30-60 minutes, and the survey is expected to last no more than 10 minutes. The text message writing activity is expected to last no more than one hour. The peer video activity is expected to take no longer than one hour. The meaningful stories writing activity is expected to last no more than one hour. In addition to the four activities, after the completion of the qualitative interviews and text message/story development, peer advisory panel members will be invited to participate in a mini-pilot to provide iterative feedback on text message frequency and content. The mini-pilot is expected to take no more than 2 weeks. We will also conduct a qualitative interview at the end of the mini-pilot; this interview is expected to take no more than one hour.

Each activity and the mini-pilot may occur independently from other activities; activities and the mini-pilot may be spread out over the course of one month.

Aim 1 key informant participants are expected to actively participate in the study for no more than one hour.

Aim 2 adolescent participants are expected to actively participate in the study for no more than six months. Once enrolled, adolescents will participate either the control or intervention for six months. We will also conduct brief (30-60 minute) qualitative interviews with all adolescents at their six-month follow-up appointment to deepen our understanding of their experience with the V2V program and obtain specific feedback on ways to improve the program for future refinements.

Aim 2 key informant participants are expected to actively participate in the study for no more than one hour.

All study activities will take place outside of academic instructional hours.

10. STUDY ENDPOINTS*

The primary outcome for Aim 2 is the feasibility of the research protocols, including participant recruitment and retention. Secondary outcomes include: preliminary effect size estimates of the intervention on cotinine-validated 7-day point prevalence abstinence, time to first quit attempt, and amount of use; acceptability of and satisfaction with the intervention; system use and adoption of cessation supporting strategies; Social Cognitive Theory (SCT) constructs; and demographics and tobacco use.

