Enrollment: Interested adolescents whose parents (or legal guardians) have not opted out, or who are 18 or older, will meet with the Research Coordinator in the privacy of the high school nurse's office. The adolescent will not meet with the school nurse. After a brief screening, assent, or informed consent if the student is 18 years of age or older, will be explained such that students understand they have a right to refuse to participate, that their care in the school health clinic and their grades will not be affected by whether or not they decide to participate, and confidentiality will be emphasized. *See also #30, Consent Process.* The screening form will be submitted to the IRB for review and approval prior to use in the study.

Study Activities:

Trial: The control group will be provided written e-cigarette cessation materials. To the intervention group, we will provide access to the V2V toolkit, including access to peer coaches and peer messaging, detail how the peer messages and videos were pre-developed and set expectations for the response time from their peer coaches.

Baseline (study entry) and 6-month follow-up data will be collected from all enrolled Aim 2 participants in the privacy of the school nurse's office. Baseline and 6-month data collection forms will be submitted to the IRB for review and approval prior to use in the study; see Table 2 for a description of data to be collected. We have also included measures in the baseline and 6-month data collection forms to assess psychosocial factors (including the Perceived Stress Scale

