With participant permission, we will collect complete and accurate contact information from the student at baseline, including home address, phone, cell phone, email, and phone numbers of three contacts and best times and days to reach them to maximize retention. A contact sheet will be completed by the participant that will include the above information. Care will be taken to maintain the confidentiality of the student's participation; therefore all students will be asked to provide us with the individuals or contact information where they feel comfortable being contacted by study staff or where they feel assured that the confidentiality of their participation will be maintained. The other contacts provided by the student will not be informed of the student's vaping status. We have found in prior studies that cell phone numbers and e-mail addresses are particularly helpful in remaining in contact with this population. Tracking procedures will be implemented for any student who does not attend a scheduled study visit or who is not accessible by telephone or e-mail at the contact location provided. Attempts to locate students will be made mainly through the schools and by telephone calls to the contacts provided or directory assistance.

Table 2. Study Assessments, Measures and Data Collection Timing

Variable and Measure	Relevant Aim	Baseline	6-month follow-up
Recruitment: # screened and eligible, # and reasons for refusal	2A	•	
Retention: # of dropouts, reasons for dropping out	2A		•
Engagement (V2V only): # of completed responses to texting quizzes, peer videos viewed, peer coaching interactions	2B		*
Acceptability and satisfaction: Client Satisfaction Questionnaire (CSQ-8) semi-structured interview	2B		•
Cotinine-validated 7-day point prevalence abstinence: saliva samples collected from all; analyzed for those reporting 7-day abstinence; cut-off 11.4 ng/ml	2C		•
E-cigarette use frequency (past 7 and 30 day) and intensity (# days and amount vaped in past 7 and 30 day)	2C	•	•
THC/marijuana and other tobacco use frequency (past 7 and 30 day) and intensity (# days and amount vaped)		•	•
Social Cognitive Theory (SCT) constructs			
Self-efficacy, confidence to quit: Self-efficacy Questionnaire (SEQ-12)		•	•
Demographics and tobacco use			
Demographics: age, gender, socio-economic status, race/ethnicity, grade in school, academic performance		•	•
History of all tobacco use, past and recent quit attempts, cessation strategies used		•	

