Attitudes about e-cigarette and other tobacco use		•	•
Stage of change: Prochaska's Stages of Change		•	•
Severity of nicotine addiction: Hooked on Nicotine Checklist (HONC) (adapted for vaping)		•	•

Semi-Structured Interviews: In addition to the above assessments, we will conduct brief qualitative interviews with all intervention participants after they have completed six-month follow-up to deepen our understanding of their experience with the V2V program and obtain

specific feedback on ways to improve the program for future refinements. The interviews will examine a series of topics, including constructs from our hypothesized conceptual model, as well as participant perceptions of each of the V2V components, message content, and system usability. Across these topics, our goal will be to understand what participants most valued and to elicit recommendations for further intervention enhancement. Interviews will be semi-structured, allowing for natural conversation with opportunities to explore unanticipated issues. We anticipate interviews to be no more than 60 minutes in duration. The interview guides will be submitted to the IRB for review and approval prior to use in the study.

Compensation: Gift cards worth \$25 will be provided to adolescents for completion of each assessment (baseline and 6-months; \$50 total).

Key Informant Recruitment and Enrollment:

Recruitment of eight key informants (school nurse, Vice Principal, or other academic administrator) will take place in-person at the high school. We are requesting a waiver of document of consent for the key informants. We will provide key informants with a fact sheet.

Semi-Structured Interviews with Adult Key informants: We will employ semi-structured individual interviews with the school nurse, vice principal, or other academic administrator (minimum of 2 key informants) from each participating high school. We will develop two complementary interview guides, one for adolescents and one for adult key informants. The interview guides will be submitted to the IRB for review and approval prior to use in the study. The semi-structured interview is expected to last no more than 60 minutes.

Compensation: Gift cards of \$100 will also be provided to the key informants (school nurse, Vice Principal, or other academic administrator).

See also #30, *Consent Process* and #9, *Study Timelines*.

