Aim 2C (Cessation Outcomes) *Hypothesis H2: The intervention will be associated with greater cotinine-validated 7-day point prevalence vaping abstinence rates, lower time to first quit attempt, and less amount of e-cigarette use compared to control at 6-month follow-up.* We recognize that there is some controversy about estimating effect sizes from pilot studies. However, we are calculating effect sizes in our study to provide a range, recognizing that there might be uncertainties because of our small sample size. To estimate effect sizes for V2V intervention versus control, between-condition differences over time will be estimated for **cotinine-validated 7-day point prevalence abstinence** using GEE logistic regression with a random effect for school and fixed effects of condition, time point (baseline and 6 months), and their interaction. Missing data is handled using inverse probability weighting. By taking the repeated measurements into consideration, the GEE model is able to increase the power to test the difference in the outcome. COX regression modeling will be used to examine the intervention effect on **time to first quit attempt** adjusting for other covariates. **Amount of e-cigarette use** will be calculated as a reduction from baseline. We will model this reduction using negative binomial regression modeling if the variance of the distribution of risk reduction is over dispersed.

Other information important for the design of a future study includes standard deviations, as well as **preliminary assessment of possible mediators** such as engagement, behavioral capability, and self-efficacy. We will identify important mediators in exploratory analyses. Guided by the conceptual model based on SCT, we will assess effects of intervention on the mediator and the

effects of the mediator on the outcome, controlling for other mediators in the model, and confounders of the mediator-outcome relationship, and then estimate the proportion of the intervention effect explained. Given the limited sample size, conclusions from the mediation analyses will be limited and treated with caution, but modeling will allow us to explore the constructs of SCT and potential predictors towards a larger RCT.

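### Adoption of cessation strategies is a secondary outcome, but the assessment table records strategies only at baseline, and behavioral capability is a planned mediator with no named measure

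*Combined protocol and SAP*

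**What the plan says.** **Outcomes.** Section 10 (Study Endpoints) gives feasibility as the primary outcome for Aim 2. Its secondary outcomes include "system use and adoption of cessation supporting strategies; Social Cognitive Theory (SCT) constructs".

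**Data collection.** Section 11 (Procedures Involved) says of the baseline and 6-month forms: "see Table 2 for a description of data to be collected". In Table 2 the only row that mentions strategies is "History of all tobacco use, past and recent quit attempts, cessation strategies used". It has a baseline mark and no 6-month mark. Under the heading for Social Cognitive Theory constructs there is one row, "Self-efficacy, confidence to quit: Self-efficacy Questionnaire (SEQ-12)", marked at both visits. System use is covered by "Engagement (V2V only): # of completed responses to texting quizzes, peer videos viewed, peer coaching interactions".

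**Analysis.** Section 13, Aim 2C, plans a preliminary assessment of mediators "such as engagement, behavioral capability, and self-efficacy". It intends to estimate the effect of the intervention on the mediator, the effect of the mediator on the outcome with other mediators and confounders controlled, and the share of the intervention effect explained. Section 13 describes no analysis of strategy adoption.

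**The concern.** Adoption means taking something up after it has been offered. A value recorded only at study entry, before either condition has started, describes past behaviour and cannot show uptake. Section 4 states that the tools are meant to help adolescents use strategies for managing cravings and quitting. Whether V2V changes strategy use more than written materials do is therefore close to the purpose of the intervention, and the answer would inform the larger trial that this pilot is meant to prepare.

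Behavioral capability raises a similar problem. The mediation steps in Section 13 each need a scored variable per participant, and none is named for this construct.

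If the 6-month form follows Table 2, the gap is hard to repair later, because what participants did between baseline and 6 months cannot be reliably reconstructed once follow-up has closed.

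**Working it through.** No sample size, power or error rate enters this point. The check sets the outcome and mediator lists against the rows and timing marks of Table 2, then looks for any other source.

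| Item in the plan | Where named | Row in Table 2 | Baseline | 6 months | Arms |
|---|---|---|---|---|---|
| System use | Section 10 | Engagement | no | yes | V2V only |
| Strategy adoption | Section 10 | Tobacco-use history row, strategies item | yes | **no** | all |
| Self-efficacy | Section 13, Aim 2C; Table 2 | SEQ-12 | yes | yes | all |
| Behavioral capability | Section 13, Aim 2C | **none** | – | – | – |

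**Step 1: is the blank deliberate?** The table does use its timing columns to distinguish rows. Recruitment is marked at baseline only, retention at 6 months only, and attitudes, stage of change and the nicotine dependence checklist at both visits. The strategies row has a baseline mark alone. It reads as a history item taken once.

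**Step 2: could another source supply strategy use after baseline?**

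- *Engagement data.* These count quiz responses, videos viewed and coaching contacts. They show use of the tools, not which quitting strategies a participant took up, and they do not exist for the control arm.
- *Texting quizzes.* Section 11 sends them over the 6 months, but their content is not described. Section 13 uses them only as a percentage completed.
- *Interviews at 6 months.* Section 11 says: "The interviews will examine a series of topics, including constructs from our hypothesized conceptual model". Section 13 codes them thematically, so they give no planned score. Section 11 assigns them to intervention participants, while Sections 9 and 13 say all participants, so even their coverage of the control arm is unsettled.

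**Step 3: count.** Table 2 has 1 item on strategies, with 0 follow-up marks. It has 1 row under the Social Cognitive Theory heading and 0 rows for behavioral capability. Section 13 gives 3 example mediators, of which 1 has no named measure. The term behavioral capability does not occur elsewhere in the document.

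**Step 4: consequence.** With a baseline value only, neither change within a condition nor a difference between conditions in strategy use can be estimated. With no behavioral capability variable, none of the three mediation quantities can be computed for it.

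**The case against.** Five arguments can be made against the point.

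1. **Table 2 is not a full inventory of the forms.** Section 11 says: "We have also included measures in the baseline and 6-month data collection forms to assess psychosocial factors", naming a stress scale and a depression scale, and neither is in Table 2. A reader might infer from the table that no participant will have a post-baseline value for strategies, or any value for behavioral capability. The documents do not support that, because the forms are not shown. What stands is narrower: no such measure is named. The two extra scales are disclosed in the text, whereas nothing comparable is said about strategies or behavioral capability.

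2. **Some evidence will exist.** The interviews may touch on model constructs, and quiz answers might mention strategies. A reader might therefore go too far in saying that neither topic can be evaluated at all. The supportable statement is that neither can be evaluated quantitatively as documented.

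3. **The outcome could mean uptake of V2V itself.** System use and strategy adoption share one entry in Section 10, and the phrase might refer to messages, videos and coaching. On any reading, system use is measured in the V2V arm, so a reader who concludes that a whole secondary outcome is lost goes too far. But Section 4 treats strategies as things adolescents do with help from the tools, and Table 2 uses the word for participants' own quitting behaviour. If the sponsor intends the narrower meaning, Section 10 should say so.

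4. **The mediation work is exploratory.** Section 13 offers the mediators as examples and promises caution in interpreting them. This is right and limits the weight of that part. It does not supply the missing variable.

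5. **A strategy count could stand in for behavioral capability.** The documents do not support this. They do not define the construct, equate it with strategy use, or describe the strategies item as a count. The substitution would also make one variable both an outcome and a mediator.

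**Conclusion.** The point holds as a mismatch between the outcome and mediator lists and the assessment schedule. As documented, strategy adoption has no scored follow-up measure in either condition and so cannot be estimated or compared. Behavioral capability has no named measure at any visit.

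The size is limited: half of one secondary outcome entry and one of three example mediators. System use is measured in the V2V arm, and self-efficacy is measured at both visits. The primary feasibility outcome, and the sample size that rests on retention, are not affected.

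The conclusion assumes that the 6-month form follows Table 2 and that strategy adoption means participants' own quitting behaviour. If the form already holds the items, the defect is only in the documentation. The change is still worth making before follow-up, because it is small and the data are hard to recover afterwards.

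**What to change.** **First, check the 6-month form.** If it already asks about strategies used, or already holds a behavioral capability measure, correct Table 2 and Section 13 to say so.

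**Strategy adoption.** Otherwise, mark the strategies item at 6 months as well as baseline, in both conditions. The follow-up version should ask about the period since enrolment. Giving the item its own row in Table 2 would avoid repeating the whole history question. Add a sentence to Section 13 saying that it will be reported by condition.

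**Behavioral capability.** Either name a measure collected at baseline and 6 months, or remove the term from the mediator list in Section 13. Do not use the strategy item in its place by default.

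**Cost.** The strategy change is one existing item asked a second time. Section 11 limits the survey to 15-20 minutes, plans a pre-test against that limit, and says the forms go to the IRB before use, so both steps can absorb the change. Removing behavioral capability costs nothing at the visit; adding a measure for it costs whatever time that instrument takes at two visits and should go through the same pre-test.
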